5.1. Benefit-to Risk rationale

The outcome of the risk management process for the clinical study including the use of the investigational device is that the medical benefits of the device outweigh the risks associated with its use.

There is no unacceptable risk when participating in the clinical study with the AirWaze investigational device. The residual risks for the investigational device use are low and therefore outweighed by the medical benefits as outlined above. The investigational device can be safely used in clinical practice.

6. Objectives

6.1. Primary objective

The primary objectives of this feasibility clinical investigation are to assess the overall system usability of the Philips AirWaze investigational device as measured by the System Usability Score (SUS) and the accuracy of the tool-in-lesion confirmation scan CBCT-FluoroSweep compared to the conventional CBCT.

6.2. Secondary objective(s)

The secondary objectives of this clinical feasibility investigation are:

- To assess intuitiveness of the individual AirWaze features by the physicians.
- To assess performance the following developed algorithms:
 - (a) Segmentation bronchial tree on pre-procedural CT.
 - (b) Elastic registration of the intraoperative CBCT scans with preprocedural CT scan.
 - (c) Automatic device detection on intraoperative CBCT scans.
- To assess the quality of the interventional plan (pre-procedural planning).
- To assess the confidence levels of interventional pulmonologists while using AirWaze (pre-procedural planning).
- To assess the intraprocedural cognitive load of CBCT-guided NB.
- To determine the radiation exposure for patients and staff.
- Report all adverse events, adverse device effects and device deficiencies.

IGT Systems	Feasibility Clinical Investigation Protocol AirWaze – easy and advanced tools for CBCT guided lung interventions	Doc ID: XCY607-130895 Rev: 04 Date: 2024-Jun-19 Page 19 of 56
-------------	--	--

7. Study Design

7.1. General

The AirWaze software tools for CBCT-guided diagnosis of peripheral pulmonary nodules will be studied at the Radboud University Medical Centre with the Principal Investigator described below:

Name Principal Investigator(s)	Name and address investigation site(s)
[name], MD, PhD Professor of Interventional Pulmonology	Radboud University Medical Center Nijmegen Department of Pulmonary Diseases [name], The Netherlands

An interview guide will be used to collect data regarding the primary endpoint. Data about the primary endpoints will be collected with semi-structured interviews as described in Appendix I: System Usability Scale (SUS) and Appendix II: CBCT-FS compared to CBCT.

A total of 37 prospectively included subjects in the Intention-To-Treat population are necessary to collect sufficient data for the evaluation of the objectives of this clinical investigation. After applying a drop-out rate of 10% of subjects will be lost, a total of 33 subjects in the Per Protocol population is required. More information on the statistical considerations can be found in Section 8.

7.1.1. Endpoints

The primary and secondary endpoints are based on the objectives (Section 6) and are described below.

Primary endpoints

The system usability will be assessed by using the System Usability Scale (SUS) ¹⁵. An average SUS of greater than 70 will indicate a good usability design of the AirWaze Software solution. The SUS will be measured per operator every 4 procedures.

Image-based tool-in-lesion confirmation accuracy of CBCT-FS is defined as the number of procedures where CBCT-FS scans were adequate to define tool-in-lesion compared to conventional CBCT scans (gold-standard). The image-based tool-in-lesion accuracy is defined as the sum of the number of tool-in-lesion in both the CBCT-FS and CBCT images (i.e. true positives), and the number of no tool-in-lesion confirmation in both the CBCT-FS and CBCT images (i.e. true negatives), divided by the total number of CBCT-FS and CBCT pairs. Image based tool-in-lesion confirmation accuracy of 90% will indicate that the CBCT-FS is postulated to be sufficient for navigation bronchoscopy.

IGT Systems	Feasibility Clinical Investigation Protocol AirWaze – easy and advanced tools for CBCT guided lung interventions	Doc ID: XCY607-130895 Rev: 04 Date: 2024-Jun-19 Page 20 of 56
-------------	--	--

Secondary endpoints

The secondary endpoints of this feasibility clinical investigation are:

- Semi-structured questionnaires to assess intuitiveness of AirWaze features for CBCT-guided biopsy of peripheral pulmonary nodules (Appendix III).
- Quantitative and qualitative assessment of the developed algorithms is assessed through a questionnaire (Appendix IV).
 - (a) Segmentation bronchial tree on pre-procedural CT.
 - (b) Elastic registration of the intraoperative CBCT scans with preprocedural CT scan.
 - (c) Automatic device detection on intraoperative CBCT scans.
- The quality of the interventional planning is defined by comparing the pre-procedural planned navigation trajectory compared to the actual navigation trajectory towards the first lesion (Appendix V).
- Confidence levels of pulmonologists are defined as a score (0-10) to examine the degree of confidence of specialists regarding: (i) the localization of the lesion and planned navigation trajectory; (ii) reaching the first pulmonary lesion based on the planning (Appendix V).
- The cognitive load of pulmonologists during the navigation towards the first lesion will be measured with the Surgical Task Load Index (SURG-TLX) which is a validated method for measuring cognitive load. The questionnaire is asked after tool-in-lesion confirmation (either rEBUS, CBCT, or CBCT-FS) ^{12,16,17} (Appendix V).
- Radiation exposure for patients will be measured in effective dose (mSv) and DAP (Gy·cm²) per procedure including fluoroscopy, CBCT and CBCT-FS radiation dose. The fluoroscopy time (minutes) will be measured as well (Appendix V).
- Radiation exposure for the staff is measured in an average scattered effective dose (mSv) per procedure at hand and chest (Appendix V).
- Report all adverse events (including but not limited to pneumonia, pneumothorax, bleeding/hemorrhage).
- Report all adverse device effects.
- Report all device deficiencies. Device deficiencies that could have led to an SAE need to be reported in the Clinical Study End Report.

7.1.2. Maintenance and calibration

The equipment relevant for the assessment of the clinical investigation is the Philips Azurion C-arm system. Maintenance and calibration of this equipment will be monitored if this is appropriately performed and documented.

7.1.3. Operators / users

In the pre-procedural evaluation of the AirWaze software device, at least three users (n=3) (e.g. interventional pulmonologist experts) will be performing the pre-procedural planning of the CBCT guided peripheral pulmonary nodules biopsies. In the peri-procedural evaluation of the AirWaze software device, at least three certified bronchoscopists (n=3) (e.g. interventional pulmonologist experts) will be performing CBCT guided biopsies of peripheral pulmonary nodules biopsies.

7.2. Investigational device exposure and comparators

During this study, a single investigational device (the AirWaze software device) will be used in this clinical trial, from the Philips workstation connected to the Philips Azurion. The AirWaze device will be used for procedural planning, image-guided navigation, and tool-in-lesion confirmation for bronchoscopic biopsy.

IGT Systems	Feasibility Clinical Investigation Protocol AirWaze – easy and advanced tools for CBCT guided lung interventions	Doc ID: XCY607-130895 Rev: 04 Date: 2024-Jun-19 Page 21 of 56
-------------	--	--

7.3. Subjects

7.3.1. Inclusion and exclusion criteria

In- and exclusion criteria ensure the inclusion of subjects within the intended patient population of the investigational device.

7.3.1.1. Inclusion criteria

In order to be eligible to participate in this study, a subject must meet the following criteria:

- Age 18 years or older at the time of informed consent.
- ASA physical status between 1 and 3.
- Subject is willing and able to give written informed consent for clinical investigation participation prior to the procedure.
- Subject has a pulmonary lesion (e.g. a focal rounded opacity mostly surrounded by aerated lung or a ground glass opacity or part- or (sub)solid lesion) with an indication for diagnostic evaluation following current clinical guidelines and/or as decided by multi-disciplinary team consultation.
- Suitable for CBCT-guided endobronchial nodule biopsy under general anaesthesia.
- Pre-procedural (PET-)CT scan is immediately available prior to procedure.

7.3.1.2. Exclusion criteria

A potential subject who meets any of the following criteria will be excluded from participation in this study:

- Aged 17 or younger at the time of informed consent.
- ASA physical status is equal to and greater than 4.
- Not willing or not able to give informed consent.
- Does not indicate diagnostic evaluation with navigation bronchoscopy.
- Not suitable for CBCT-guided endobronchial nodule biopsy via navigation bronchoscopy under general anaesthesia.
- There is no recent pre-procedural (PET-)CT scan available.
- Known bleeding disorders.
- Contra-indication for temporary interruption of the use of anticoagulant therapy (acenocoumarol, warfarin, therapeutic dose of low molecular weight heparins, clopidogrel or analogues, NOACs).
- Known allergy for lidocaine or other allergies interfering with the procedure.
- Uncontrolled pulmonary hypertension.
- Recent and/or uncontrolled cardiac disease.
- Compromised upper airway (e.g. concomitant head and neck cancer or central airway stenosis for any reason such that endobronchial access is considered unsafe).
- Potentially confounding drug or device trial clinical study. Co-enrollment in concurrent trials may be allowed if pre-approval is obtained from Philips Clinical Study Manager.
- All vulnerable subjects, such as immune-compromised subjects, subjects lacking the capacity to provide consent, patients in emergencies, pregnant or breastfeeding women, or any other subject who meets exclusion criteria, according to applicable national laws, if any.
- Woman of childbearing potential who is known to be pregnant on admission.
- Any condition that in the judgment of the investigator could impose hazards to the patient if study therapy is initiated or affect the participation of the subject in the study.
- Subject is Philips employee or their family members residing with this Philips employee.

7.3.2. Enrollment and duration

The total duration of the study is expected to take approximately 18 months, from the first patient to the last patient (excluding reporting). The first patient was enrolled in October 2023.

- Subjects are enrolled in the feasibility clinical investigation after they have signed the informed consent form. No study procedures will be performed before this moment.

IGT Systems	Feasibility Clinical Investigation Protocol	Doc ID: XCY607-130895
	AirWaze – easy and advanced tools for CBCT guided lung interventions	Rev: 04 Date: 2024-Jun-19 Page 22 of 56

- Subjects are enrolled in the clinical investigation for the duration of the interventional procedure until 1 week post-procedure. A safety follow-up visit (either by phone or clinic visit) will take place at 1 week (-2 days/+7 days) post procedure.

The clinical investigation is completed when the last subject has undergone CBCT-guided NB and follow-up visit, whether the clinical investigation concluded according to the pre-specified clinical investigation plan or was terminated prematurely.

7.3.3. Number of subjects

A total of 37 prospectively included subjects in the Intention-To-Treat population are necessary to collect sufficient data for the evaluation of the primary and secondary objectives of this clinical investigation. After applying a drop-out rate of 10% of subjects will be lost, a total of 33 subjects in the Per Protocol population is required. More information on the statistical considerations can be found in Section 8.

7.3.4. Procedure for the replacement of subjects

Subjects in the study will be replaced in case of withdrawal of consent or the subject is found illegible for the study after signing the informed consent and before the procedure. The data of these subjects will not be analyzed (per protocol analysis, see section “statistical considerations”).

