7.4. Procedures

The flowchart for current clinical practice and study practice CBCT-guided navigation bronchoscopy are depicted in *Figure 3* below.

Current clinical practice

- Pre-procedural*

In current clinical practice, the lesion identification and trajectory planning are performed by interventional pulmonologists who need to mentally reconstruct the navigation trajectory (mind-map) based on the available CT-images in routine DICOM viewers.

- Intra-procedural*

The procedure starts with an inspection bronchoscopy to examine the trachea and proximal airways. If the tumour is not visible endobronchially, navigation bronchoscopy is continued by advancing a pre-formed curvature catheter through the bronchoscope under image guidance. Advanced imaging with CBCT and AF will expedite catheter guidance through the airways. The CBCT gives feedback about the position of the catheter in a three-dimensional space. Once tool-in-lesion is confirmed with either rEBUS, rapid on-site evaluation (ROSE) and/or CBCT, tissue sampling is performed. If indicated, an EBUS is performed for staging lung cancer.

Study practice

- Pre-procedural*

In this study, pre-procedural planning will be performed with Philips' AirWaze software. The CT-scan is loaded into the software system and the airways will be segmented and visualized. The target lesion is segmented with a one-click segmentation by the physician and is followed by a selection of the pathway to the target lesion.

IGT Systems	Feasibility Clinical Investigation Protocol AirWaze – easy and advanced tools for CBCT guided lung interventions	Doc ID: XCY607-130895 Rev: 04 Date: 2024-Jun-19 Page 23 of 56
-------------	--	--

- *Intra-procedural*

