8.1. Analysis Populations

The following analysis populations will be defined in this study:

Enrolled Population

The enrolled population is defined as all subjects who signed informed consent during the study.

Intention-to-treat Population

The intention-to-treat population (ITT) is defined as all subjects in the Enrolled Population that have undergone the CBCT-guided navigation bronchoscopy procedure as depicted in *Figure 3* because suspected pulmonary lesions with intermediate to high risk of malignancy in early-stage disease were found on pre-procedural CT scans.

Per Protocol population

The Per Protocol population (PP) is defined as all ITT subjects without major protocol deviations. Protocol deviations will be divided into major protocol and minor protocol deviations. A major protocol deviation is one that may impact subject safety, affect the integrity of study data and/or affect subject's willingness to remain in the study. An example of a major violation is enrolling a participant who did not meet all the inclusion/exclusion criteria or failing to obtain or document informed consent prior to initiation of study procedures. Major protocol deviations would exclude the subject from the PP population.

Minor protocol deviations are those that are not considered to significantly affect the primary endpoint analysis and hence do not warrant subjects' exclusion from the PP population.

Subjects with a tumor location endobronchial found during the inspection bronchoscopy and therefore not require the CBCT-guided navigation bronchoscopy (as displayed in *Figure 3*), will be excluded from the PP population.

The PP population will be the primary population for the analyses as described in study objectives and endpoints.

IGT Systems	Feasibility Clinical Investigation Protocol AirWaze – easy and advanced tools for CBCT guided lung interventions	Doc ID: XCY607-130895 Rev: 04 Date: 2024-Jun-19 Page 25 of 56
-------------	--	--

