- Quality of the automatic device detection is considered sufficient when the average Likert score equals or is higher than 4. For this categorical variable, counts and percentages will be calculated as well.
- Algorithm failures are acceptable when in <5 % of the cases for pulmonary lesions algorithm failures related to CBCT or CBCT-FS occurred.

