8.7.4. Secondary objective: Confidence level

Objective

To assess the confidence levels of interventional pulmonologists while using AirWaze (pre-procedural planning).

Endpoint

Confidence levels of pulmonologists are defined as a score (0-10) to examine the degree of confidence of specialists regarding:

- 1) the localization of the lesion and planned navigation trajectory.
- 2) reaching the first pulmonary lesion based on the planning.

Analysis

The level of confidence is scored between 0 and 10, respectively (not confident to very confident). The analysis includes a calculation of the mean, median and standard deviation assuming a normal distribution. This objective succeeds if the mean confidence level is 6.5 or higher for both confidence level scorings. More information about the confidence level can be found in

IGT Systems	Feasibility Clinical Investigation Protocol	Doc ID: XCY607-130895
	AirWaze – easy and advanced tools for CBCT guided lung interventions	Rev: 04 Date: 2024-Jun-19 Page 29 of 56

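### The pre-procedural AirWaze endpoints are analysed only in subjects who went on to the bronchoscopy, so selection on the planning result is possible

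*Combined protocol and SAP*

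**What the plan says.** - **Order of events.** Section 7.3.2 enrols subjects at signature of consent and adds "No study procedures will be performed before this moment". Section 7.4 then says "In this study, pre-procedural planning will be performed with Philips' AirWaze software". Planning therefore comes after consent and before the bronchoscopy; no interval is given.
- **Replacement.** Section 7.3.4 gives two grounds: "Subjects in the study will be replaced in case of withdrawal of consent or the subject is found illegible for the study after signing", the latter limited to the time before the procedure (the printed word is evidently meant as ineligible). On their data it says: "The data of these subjects will not be analyzed (per protocol analysis, see section “statistical considerations".
- **Eligibility.** One exclusion criterion in 7.3.1.2 is "Not suitable for CBCT-guided endobronchial nodule biopsy via navigation bronchoscopy under general anaesthesia".
- **Analysis sets.** In 8.1, ITT is "all subjects in the Enrolled Population that have undergone the CBCT-guided navigation bronchoscopy procedure". PP is a subset of ITT and is the primary set for the analyses.
- **Cut-offs.** Section 8.7.4: "This objective succeeds if the mean confidence level is 6.5 or higher for both confidence level scorings". Section 8.7.2 calls segmentation quality sufficient at a mean Likert score of 4 or more, and adds: "Algorithm failures are acceptable when in <5 % of the cases for pulmonary lesions algorithm failures related to CBCT or CBCT-FS occurred".
- **Forms.** Both confidence scores are on the pre-procedural planning form (Appendix V, Part A, items 9 and 11). The segmentation rating is in Appendix IV, which is completed after each procedure.

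**The concern.** The confidence scores and the quality of the airway segmentation are results of planning. Neither needs a bronchoscopy to exist. Yet a subject who is planned and then not treated has no place in ITT or PP, and if the exit is a withdrawal or an ineligibility finding, 7.3.4 also says that the data are not analysed. Switching from PP to ITT does not bring the subject back.

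One ground for ineligibility is unsuitability for the navigation procedure, and that judgement can be made until the procedure starts. The plan does not require it to be fixed before the AirWaze plan is seen, or to be made independently of it. If a failed segmentation or a low-confidence plan influenced the judgement, the subject would leave the very endpoints on which AirWaze planning is judged, and the replacement would come from those who proceeded. Confidence and segmentation scores would then be too high and the failure percentage too low. This matters because 8.2 describes the study as de-risking and says that algorithm failures will be evaluated.

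**Working it through.** **1. The plan's own figure.** Inputs from 7.3.3: 33 PP subjects and 10% drop-out. 33 / (1 − 0.10) = 36.67, rounded up to 37. The stated 37 is reproduced. It is an ITT number, so the 10% allowance covers loss from ITT to PP. Subjects who leave before the procedure are never in ITT. They lie outside the allowance, and no limit is set on their number.

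**2. Which endpoints are affected.**
- Confidence scores: recorded before the procedure, analysed only if the procedure follows.
- Segmentation score and segmentation failure: produced from the pre-procedural CT, but rated on a form completed after the procedure. A subject planned and not treated has no scheduled rating.
- Trajectory match (8.7.3): the denominator is performed navigations, so an untreated subject cannot contribute by construction. Not affected.

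**3. Possible size.** Let k be the number of planned subjects left out. The documents give no value; k = 1 to 4 is assumed, with 33 analysed.

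Failures, (f + k) / (33 + k), if every excluded subject is a segmentation failure:
- f = 1: 1/33 = 3.0% meets the limit; k = 1 gives 2/34 = 5.9%, which does not.
- f = 0: k = 1 gives 1/34 = 2.9%, still acceptable; k = 2 gives 2/35 = 5.7%, not acceptable.

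This applies the 5% rule to segmentation failures. The endpoint definition in 8.7.2 includes failed segmentation of the preoperative CT, although the rule itself refers to CBCT and CBCT-FS.

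Confidence, worst case (excluded plans scored 0). The observed mean needed for the full group to reach 6.5 is 6.5 × (33 + k) / 33:
- k = 1: 6.70
- k = 2: 6.89
- k = 4: 7.29

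Confidence, less extreme case (two excluded plans scored 3):
- observed mean 6.6: (33 × 6.6 + 6) / 35 = 6.39, a change of verdict
- observed mean 7.0: (33 × 7.0 + 6) / 35 = 6.77, no change

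Segmentation score, worst case (excluded plans scored 1). The observed mean needed to reach 4 is (4 × (33 + k) − k) / 33:
- k = 1: 4.09
- k = 2: 4.18
- k = 4: 4.36

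The failure percentage is thus sensitive to one or two subjects. The means change verdict only when they lie close to the cut-off.

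**The case against.** A reader might infer that planning failures lead to cancelled bronchoscopies and that the device output behind them is then deleted. The documents do not support that.

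- No section says that a failed segmentation or a low-confidence plan makes a subject ineligible. Section 3.2.1 describes AirWaze as an adjunct. Table 4 in 15.3 mitigates wrong treatment decisions by a user-manual message that the feature is not meant for clinical decisions, and for a permanent malfunction during a procedure it has the user carry on without the tool. Routine planning works from CT images in ordinary viewers (7.4), so an AirWaze failure does not by itself make a patient unsuitable. The forms also expect poor plans: they offer a box for failed segmentation and confidence scores from 0.
- Section 7.3.4 names withdrawal and ineligibility, not cancellation, and either may occur before planning has been done.
- Not all trace of these subjects is lost. Data are listed for the enrolled population (8.3), reasons for non-evaluation are listed (8.4), and adverse events, device effects and device deficiencies are analysed in all subjects (8.7.7 to 8.7.9).
- Section 8.7 calls the secondary objectives descriptive, without performance requirements.

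Most of this stands, and it limits the point to a possible selection. It does not remove it. Listings do not enter the means and percentages, the cut-offs in 8.7.2 and 8.7.4 still give verdicts, and under 8.1 a planned subject without a bronchoscopy is left out of the summaries whatever the reason. The broad statement in 7.3.4 that such data are not analysed also conflicts with the all-subject analyses in 8.7.7 to 8.7.9.

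**Conclusion.** The point holds as a gap in the analysis sets. Endpoints that arise at planning are summarised only in subjects who had the bronchoscopy, and the eligibility judgement that can remove a subject is not separated from the plan. Whether this biases the results depends on two things that the documents do not give: how many subjects are planned and then not treated, and whether their plans were worse. If there are none, nothing changes. If there is one, and it is a segmentation failure, a failure rate of 3.0% becomes 5.9% and crosses the limit; a confidence mean well above 6.5 would keep its verdict. The primary endpoints are not affected. This is an inexpensive improvement to descriptive secondary endpoints, not a flaw that undermines the study.

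**What to change.** - **8.1:** add a planned set of all enrolled subjects whose CT was loaded into AirWaze, leaving out data that may not be used after consent withdrawal.
- **8.7.4 and 8.7.2:** use this set for both confidence scores, the segmentation score and segmentation failures. Keep 8.7.3 on performed navigations.
- **7.3.4:** limit the exclusion from analysis to the intra-procedural endpoints, and reconcile it with the all-subject safety and deficiency analyses in 8.7.7 to 8.7.9. Replacement can continue for the intra-procedural endpoints.
- **Appendix IV:** complete the segmentation rating at planning. Without this, the new wording would have no rating to use in untreated subjects.
- **8.4:** report the number planned but not treated, with reasons, and flag those prompted by the AirWaze plan.

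The cost is text in these sections and one rating completed earlier. No extra subjects or procedures are needed. Denominators will differ slightly between pre-procedural and intra-procedural endpoints and should be shown in each table.
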